16.1.2 Safety Variables

For laboratory test values (including estradiol [girls only], and luteinizing hormone [LH], follicle-stimulating hormone [FSH]), vital signs, height, weight, Tanner staging, electrocardiogram (ECG) parameter values, GBI scores (using the 10-item mania subscale), and C-SSRS scores, missing values will be not be imputed.

16.1.3 Covid-19 impact

This study has been carried out during the pandemic of COVID-19. As a result, impact on assessments and the timing of assessments is expected. Data will be collected to evaluate the impact of COVID-19 on the conduct of the study. These data will be presented in listings and summarized if needed.

Missing visits:

Depending on the impact of COVID-19 on data collection, it will be decided whether data from missing visits due to COVID-19 will be imputed using the LOCF approach as well.

Remote visits:

Scheduled and unscheduled visits are allowed to take place remotely via voice call or voice and video call. All the data from scheduled visits recorded remotely will be included in the analysis at the designated visit. Visit windowing as explained in [Panel 6](#) above will be applied to remote visits.

A listing will be presented on the details of remote visits including which visit was conducted remotely, date of remote visit, and whether or not patient reported outcomes and clinician reported outcomes were assessed during the remote visit.

16.2 Handling Missing or Incomplete Dates/Times

16.2.1 IMP Start and Stop Dates

A missing IMP start date will be imputed with the date of baseline of Open Label Period for *De novo* patients, Rollover patients from Study 12709A;

A missing IMP start date will be imputed with the date of baseline of Double-Blind Treatment Period for Rollover patients (remitters) from Study 12712A;

A missing IMP stop date will be imputed using last attended visit date.

16.2.2 Withdrawal Date

Missing withdrawal dates will not be imputed.

16.2.3 Medication Start and Stop Dates

Following rules will be followed to classify recent and concomitant medications for each of the two periods:

Panel 7 Classification of Concomitant Medication

Medication Start Date in period	Medication Stop Date	Classification
Unknown	< Date of first dose of IMP in period	Discontinued prior to first dose of IMP in period
Unknown	\geq date of first dose of IMP in period	Started at or after first dose of IMP in period
< Date of first dose of IMP in period	Unknown	Continued after first dose of IMP in period
\geq date of first dose of IMP in period	Unknown	Started at or after first dose of IMP in period
Unknown	Unknown	Started at or after first dose of IMP in period

16.2.4 Adverse Event Start and Stop Dates

With regard to classification of adverse events with incomplete dates, the following rule will be used:

If the start date is missing for an adverse event and the stop date is prior to the first dose of IMP, the adverse event will be classified as a pre-treatment adverse event. In all other cases of an adverse event with a missing start or stop date, the adverse event will be classified as a TEAE.

For the calculation of duration, missing or incomplete start and/or stop dates will be imputed as follows:

If only day is missing in the end date of an AE, the last day of the month will be used, whereas for missing start days the first day of the month will be used.

For ongoing adverse events, the date of the last study contact will be used as the stop date for the adverse event in the calculation of duration. For other adverse events with a missing start or stop date, the duration will not be calculated.

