8.6 Safety Follow-up Visit

A safety follow-up is conducted to capture SAEs that occur during the Safety Follow-up Period as well as to follow-up on the outcome of adverse events ongoing at the end of the treatment period.

Safety follow-up for the open-label period is applicable for patients who are withdrawn or do not continue to the double-blind period: This can be a telephone contact, unless an SAE has occurred since the last visit or unless there was a clinically significant abnormal safety laboratory test value at the last visit. In such cases, safety follow-up(s) must be scheduled to allow for a medical examination and/or blood sampling. Further safety follow-up visits beyond 30 days may be needed as judged by the investigator (if further safety follow-up visits are performed, these must be recorded in the patient's medical record, and not in the eCRF).

Safety follow-up for the double-blind period: This visit should be scheduled approximately 30 days after the last dose of IMP. This can be a telephone contact, unless an SAE has occurred since the last visit or unless there was a clinically significant abnormal safety laboratory test value at the last visit. In such cases, safety follow-up(s) must be scheduled to allow for a medical examination and/or blood sampling. Further safety follow-up visits beyond 30 days may be needed as judged by the investigator (if further safety follow-up visits are performed, these must be recorded in the patient's medical record, and not in the eCRF).

For adverse events that were ongoing at the end of the treatment period and that resolved during the Safety Follow-up Period, the stop date must be recorded. For non-serious adverse events still ongoing at the safety follow-up, the *Ongoing Adverse Event* checkbox on the *Adverse Event Form* must be ticked. SAEs must be followed until resolution or the outcome is known.

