12.1.3 Classification of Adverse Events

Adverse events will be classified according to the time of onset of the adverse event:

- *pre-treatment adverse event* – an adverse event that starts on or after the date the patient signed the *Informed Consent Form* and prior to the date of first dose of IMP. As such, this definition will only be used for *de novo* patients.
- *treatment-emergent adverse event (TEAE)* – *an adverse event that starts or increases in intensity and/or seriousness on or after the date of first dose of IMP*

Adverse events, sorted by system organ class (SOC) and preferred term, will be summarized by treatment group.

An adverse event is considered causally related to the use of the IMP when the causality assessment by the investigator is *probable* or *possible*. For pre-treatment adverse events, a causality assessment is not relevant.

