12.1.4 Allocation of TEAEs to Treatment Periods

TEAEs will be allocated to treatment periods according to the time of onset of the adverse event:

Pre-treatment AEs – an adverse event that starts on or after the date the patient signed the Informed Consent Form and prior to the date of first dose of IMP in Open Label Period. This definition will only be used for *de novo* patients.

TEAE in the Open Label Period – an AE that starts on or after the date of the first IMP intake in the Open Label Period and before the date of the end of Open Label Period. In addition, for *de novo* patients only, this also includes AEs that start before the date of the start of Open Label Period and worsens before the date of the end of the Open Label Period.

TEAE in the Double-Blind Treatment Period – a TEAE that starts on or after the date of the first IMP intake in the Double-Blind Treatment Period and before the date of the end of Double-Blind Treatment Period, **OR** starts before the date of the start of Double-Blind Treatment Period and worsens on or after the date of the first IMP intake in the DB treatment period and before the date of the end of the Double-Blind Treatment Period

TEAE in the Safety Follow-up Period – an AE that starts on or after the date of the end of Double-Blind Treatment Period or on or after the date of withdrawal (in either the Open Label Period or the Double-Blind Treatment Period).

Adverse events that are ongoing in either parent study at the time of entry into the current study will be included in the present study. All data will be transcribed and the rules as described above will apply.

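### SAP 16.2.4 labels an adverse event with a known pre-dose start and no stop date as treatment-emergent even if it never worsened, contradicting SAP 12.1.3 and 12.1.4

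*SAP*

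**What the plan says.** SAP 16.2.4 gives one route to the pre-treatment class for an event with an incomplete date: "If the start date is missing for an adverse event and the stop date is prior to the first dose of IMP". Everything else goes the other way: "In all other cases of an adverse event with a missing start or stop date, the adverse event will be classified as a TEAE".

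A separate block of 16.2.4 deals with duration. There, "For ongoing adverse events, the date of the last study contact will be used as the stop date for the adverse event", and the block ends with "For other adverse events with a missing start or stop date, the duration will not be calculated".

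The definitions are elsewhere. SAP 12.1.3 defines a TEAE as "an adverse event that starts or increases in intensity and/or seriousness on or after the date of first dose of IMP". Its pre-treatment class runs from consent to first dose: "prior to the date of first dose of IMP. As such, this definition will only be used for" de novo patients. Protocol 16.8.9 defines both classes in the same way, by onset relative to first dose, with worsening in intensity as the only other way to become a TEAE.

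SAP 12.1.4 allocates events to periods by onset or worsening. On rollover patients it says: "Adverse events that are ongoing in either parent study at the time of entry into the current study will be included in the present study". The sentence that follows applies the section's preceding rules to those transcribed events.

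**The concern.** A missing-date rule should settle only what the missing date leaves uncertain. Whether an event is treatment-emergent depends on its start, and on any later worsening. The stop date plays no part once the start is known. Yet 16.2.4 lets a missing stop date override a known start.

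Open events are routine in this study. Protocol 8.6 provides a checkbox "For non-serious adverse events still ongoing at the safety follow-up", and protocol 10.5 ends follow-up of non-serious events at that contact. Protocol 10.1.1 collects events from consent onwards, and the SAP brings in events still open from the parent studies. So events that began before first dose and have no stop date are to be expected.

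At stake are the TEAE flag in the listings, the pre-treatment summary (SAP 12.1.6) and possibly the TEAE tables (SAP 12.1.5 and 12.1.7). For a child from Study 12712A, the first dose in this study is the first double-blind dose, which may be placebo. An unchanged event that began on open-label vortioxetine could then carry a treatment-emergent flag on placebo.

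**Working it through.** The plan states no figure on this point, so the check applies 16.2.4 literally to every date pattern with at least one date missing and compares the result with 12.1.3.

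| Start date | Stop date | Class under 16.2.4 | Class under 12.1.3 | Agreement |
|---|---|---|---|---|
| missing | before first dose | pre-treatment | onset must be before first dose | yes |
| missing | on or after first dose | TEAE | cannot be determined | reasonable default |
| missing | missing | TEAE | cannot be determined | reasonable default |
| on or after first dose | missing | TEAE | TEAE | yes |
| before first dose | missing | TEAE | not a TEAE unless it worsened | **no** |

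Only the last row conflicts. The single exception in 16.2.4 requires a known stop date, so no event without one can use it.

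**Does an ongoing event count as having a missing stop date?** In 16.2.4 the sentence on ongoing events is followed at once by one on *other* events with a missing start or stop date. That wording places ongoing events among those with a missing date. The substitute stop date (last study contact) is given for the duration calculation only and does not feed back into classification.

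**Where does such an event go under 12.1.4?** Take one that started before first dose and never worsened.

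- Open-label period: it must start on or after first intake, or (de novo only) start earlier and worsen. Not met.
- Double-blind period: it must start on or after first double-blind intake, or start earlier and worsen after that intake. Not met.
- Safety follow-up: it must start at or after the end of double-blind treatment or withdrawal. Not met.

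So 16.2.4 calls it a TEAE while 12.1.4 has no treatment period for it. For a de novo child, 12.1.4 would call it pre-treatment.

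**Parallel rule.** Panel 7 in SAP 16.2.3 covers a medication with a start before first dose and an unknown stop. It is classed as continued, not as newly started, so the known start date decides.

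**Scale per child, if 16.2.4 is the rule programmed.** The planned numbers are 40 per arm (protocol 16.10) and about 150 enrolled (protocol 5.1):

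- randomized arm: 1/40 = 2.5 percentage points
- open-label period, if about 150 children enter it: 1/150 = 0.67 percentage points

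These are maxima. In the overall TEAE rate, a child with another TEAE is already counted.

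**The case against.** The strongest reply is that 12.1.4, not 16.2.4, governs the tables. The overview and the TEAE summaries are produced by period (SAP 12.1.5 and 12.1.7), and period membership requires onset or worsening. SAP 16.3.2 agrees: an event enters a second period only if its intensity increases or it becomes serious. Imported parent-study events are expressly placed under the rules of 12.1.4. This stands, and it limits the point.

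A reader might infer that the open-label incidence is inflated directly, or that carried-over events from 12712A inflate both double-blind arms and dilute the contrast. The documents do not establish either. They contain two conflicting rules and do not say which prevails.

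A second reply is that an event ticked as ongoing has a complete status and so is not missing a date. The supporting wording for the opposite view sits in the duration block, so the matter is not beyond argument. But no text exempts ongoing events, and an event with a known pre-dose start and a truly missing stop date would still be misclassified.

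A third reply is that the rule is conservative and visible: it over-counts rather than hides harm, and the listings show the start date, the TEAE flag and the period of onset. Both facts are right. But a conservative default is meant for uncertainty, and here the onset is known.

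For de novo children the exposure is also narrow. The event must start after consent, in a screening window normally of 5 to 15 days and exceptionally up to 30 (protocol 8.2), then stay open and never worsen. Such events should also seldom reach the related-TEAE tables, because SAP 12.1.3 treats causality as not relevant for pre-treatment events.

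**Conclusion.** The point holds as a defect in the stated rule. Read literally, 16.2.4 gives the wrong class to an event with a known pre-dose start, no stop date and no worsening. This contradicts SAP 12.1.3 and protocol 16.8.9, and it leaves the event without a treatment period under SAP 12.1.4. Two outputs follow 16.2.4 directly and would be wrong: the TEAE flag and the pre-treatment summary for de novo children. The period TEAE tables would be wrong only if 16.2.4 is programmed ahead of 12.1.4.

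The conclusion assumes that an ongoing event counts as having a missing stop date, which the wording of 16.2.4 favours but does not state outright. The documents give no rate of pre-existing open events and no expected split by inclusion source, so the number of children affected cannot be derived. The error is towards over-counting. The primary efficacy analysis is not touched. It should be corrected, but it does not threaten the trial's main conclusion.

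**What to change.** Amend SAP 16.2.4 to say:

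- When the start date is known, classification follows 12.1.3 and 12.1.4 whatever the stop date. A start before the first dose in the period means the event is not a TEAE of that period, unless its intensity or seriousness increases on or after that dose.
- The TEAE default applies only when the available date information cannot exclude onset on or after first dose.

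It would help to add that an event recorded as ongoing is handled by the first of these rules. The amendment should also settle one neighbouring point: 12.1.4 limits the open-label worsening branch to de novo patients, while 12.1.3 has no such limit.

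The cost is a few sentences of text and one condition in the programming of the TEAE flag. No new data are needed.

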16.3 Data with Multiple Records

16.3.1 Dose Changes in Medication

Dose changes in medications are recorded on multiple rows in the dataset, with different start and stop dates. When classifying medications into periods (prior to IMP, started or continued in treatment period), each dose is considered a separate medication, and the same medication can be assigned to several periods for the same patient. Within a period, multiple entries contribute as a single count.

16.3.2 Changes in Intensity or Seriousness of Adverse Events

Changes in adverse event intensity or seriousness are recorded on multiple rows in the dataset. When classifying adverse events into periods, an event will be assigned to more than one period only if the intensity increases or if a non-serious event becomes serious. An adverse event that changes in intensity or seriousness in a period will contribute to the count of events as a single event.

In summaries of adverse events presented by intensity, the maximum intensity of the adverse event will be used. The maximum intensity is searched for in events with changes, as well as over repeated events based on the preferred term. Adverse events for which information on intensity is missing will be classified as *severe*.

Adverse events for which information on seriousness is missing will be classified as *serious*.

References

Appendix II: Overview of Study Procedures

A) Study Procedures and Assessments – Open Label Period for *de novo* Patients and Rollover Patients from Study 12709A

Visit Name	Open Label Period										
	Screening ^a only de novo	Baseline ^b de novo	Baseline ^c 12709A rollover						Randomization	Withdrawal ^d	Safety Follow-up ^e
Visit Number	1	2	2	3	4	5	6	7	8		
Day/End of Week	d-5/d-15	0	0	W1	W2	W4	W8	W10	W12		W16
Visit Window ^f (days relative to nominal visit)		0	0	±3	±3	±3	±3	±3	±3		±5
Screening and Baseline Procedures and Assessments											
Signed Informed Assents/Consents	✓			✓							
Diagnosis (DSM-5 TM)	✓			(✓) ^g							
K-SADS-PL ^h	✓			(✓) ^g							
Disease-specific history	✓			(✓) ^g							
Relevant history (social, medical, psychiatric, neurological)	✓			(✓) ^g							
Demographics (age, sex, race)	✓			(✓) ^g							
Family psychiatric history	✓			(✓) ^g							
Traumatic life events	✓			(✓) ^g							
Inclusion/exclusion criteria	✓	✓		✓							
Randomization criteria									✓		
History of stimulant medication	✓			(✓) ^g							
Efficacy Assessments											
CDRS-R	✓	✓	(✓) ⁱ	✓	✓	✓	✓	✓	✓	✓	
CGI-S	✓	✓	(✓) ⁱ	✓	✓	✓	✓	✓	✓	✓	
PQ-LES-Q (PRO)		✓	(✓) ⁱ				✓		✓	✓	
Pharmacokinetic Assessments											
Blood sampling for vortioxetine quantification							✓		✓	✓	
Safety Assessments											
Adverse events	✓	✓	(✓) ⁱ	✓	✓	✓	✓	✓	✓	✓ ^j	
Blood and urine sampling for clinical safety laboratory tests	✓ ^k		(✓) ^{i,1}			✓			✓	✓	
Vital signs	✓	✓	(✓) ⁱ	✓	✓	✓	✓	✓	✓	✓	
Weight and height	✓		(✓) ⁱ						✓	✓	

Visit Name	Screening ^a only de novo	Baseline ^b de novo	Open Label Period								Randomization	Withdrawal ^d	Safety Follow-up ^e
			12709A rollover					3	4	5	6	7	8
Visit Number	1	2	2		3	4	5	6	7	8			
Day/End of Week	d-5/d-15	0	0		W1	W2	W4	W8	W10	W12			W16
Visit Window ^f (days relative to nominal visit)		0	0		±3	±3	±3	±3	±3	±3			±5
ECG	✓		(✓) ⁱ								✓	✓	
Examinations (physical and neurological)	✓		✓									✓	
Tanner staging and menstrual cycle	✓		✓									✓	
C-SSRS	✓	✓	(✓) ⁱ	✓	✓	✓	✓	✓	✓	✓	✓	✓	
GBI (Mania subscale)	✓	✓	(✓) ⁱ	✓	✓	✓	✓	✓	✓	✓	✓	✓	
Other Study Procedures and Assessments													
IMP dispensed			✓	✓	✓	✓	✓	✓	✓	✓	✓		
Possible change in IMP dose ^m					✓	✓	✓	✓					
IMP returned and IMP accountability					✓	✓	✓	✓	✓	✓	✓	✓	
Recent and concomitant medication	✓	✓	(✓) ⁱ	✓	✓	✓	✓	✓	✓	✓	✓	✓	
Pregnancy test ⁿ	✓		(✓) ⁱ								✓	✓	
Drug and alcohol screen ^o													

AE = adverse event; CDRS-R = Children depression rating scale revised version; CGI-S = Clinical Global Impression – Severity of Illness; C-SSRS = Columbia-Suicide Severity Rating Scale; ECG = electrocardiogram; eCRF = electronic case report form; GBI= General Behaviour Inventory; IMP = investigational medicinal product; K-SADS-PL = The Kiddie-Schedule for Affective Disorders and Schizophrenia for School-aged Children, Present and Lifetime version; PQ-LES-Q = Pediatric Quality of Life Enjoyment and Satisfaction Questionnaire – Patient rated; SAE = serious AE

- a Screening Visit will be performed only for *de novo* patients. Patients rolling over from Study 12709A will proceed directly to the Baseline Visit (see ‘Baseline Visit 12709A rollover’ column). The Informed Assent/Consent Form must be signed before any study-related activities take place.
- b Applicable only for *De novo* patients.
- c Applicable only for 12709A rollover patients. Assessments marked with (✓) in this column will be used from 12709A study and therefore not repeated.
- d This visit should take place as soon as possible after the patient withdraws from the study. Any visit during the Open Label period can be converted into a Withdrawal Visit on the day of the visit.
- e Applicable for patients withdrawn prior or at Visit 8: Safety follow-up should be scheduled approximately 30 days after the last dose of IMP. It can be a telephone contact, unless an SAE has occurred since the last visit or unless there was a clinically significant abnormal safety laboratory test value at the last visit. In such cases, safety follow-up(s) must be scheduled to allow for a medical examination and/or blood sampling. Further safety follow-up visits beyond 30 days may be needed as judged by the investigator (if further safety follow-up visits are performed, these must be recorded in the patient’s medical record, and not in the eCRF).
- f If the date of a visit does not conform to the schedule, subsequent visits should be planned to maintain the visit schedule relative to the Baseline Visit. Consider that the number of days between 2 visits must not exceed the number of days for which the patient has been dispensed IMP.
- g The data from the Screening Visit in the Study 12709A eCRF will be used.

- h The K-SADS-PL will be used to confirm diagnosis of MDD and to assess possible psychiatric co-morbidities.
- i Values from all assessments and procedures (efficacy/safety, including blood/urine samples and use of concomitant medication) performed at the Completion Visit (Visit 12) in Study 12709A will be the Baseline Visit values in Study 13546A.
- j Only for AEs ongoing at Withdrawal and new SAEs.
- k The hormones panel is to be collected at Visit 1 (estradiol in females only).
- l An extra tube of blood samples will be required for hormones at the Study 12709 Week 12 Visit.
- m Between Week 2 and Week 8, the patient and/or parents /legal representative can request an unscheduled site visit to discuss their current dose. AEs will be collected and C-SSRS, GBI-mania and CGI-S will be done at the unscheduled visit.
- n If the patient is a female patient of childbearing potential (defined as females aged ≥ 10 years old and younger girls who, at the discretion of the investigator, are deemed to be of reproductive potential), a urine pregnancy test is to be performed at screening and randomization, and at the Withdrawal Visit.
- o It is not mandatory to screen for drugs and/or alcohol. However, it can be performed at any visit, at the discretion of the investigator.

B) Study Procedures and Assessments – Double-Blind Treatment Period

Visit	Double-Blind Treatment Period (Relapse-prevention)										Safety Follow-up ^b
	Randomi- zation ^a									Completion or Withdrawal	
Visit Number	8	9	10	11	12	13	14	15	16	17	18
End of Week (relative to Baseline)	12	13	14	16	18	22	26	30	34	38	42
End of Week (relative to Randomization)	0	1	2	4	6	10	14	18	22	26	30
Visit Window ^c (days relative to nominal visit)	±3	±3	±3	±5	±5	±5	±5	±	±5	±5	±5
Randomisation Procedures and Assessments											
Signed Informed Assent/Consent (rollover patients from 12712A only)	√										
Inclusion criteria	√										
Efficacy Assessments											
CDRS-R	√ ^d	√	√	√	√	√	√	√	√	√	
CGI-S	√ ^d	√	√	√	√	√	√	√	√	√	
CGI-I		√		√		√		√		√	
PQ-LES-Q (PRO)	√			√		√		√		√	
Pharmacokinetic Assessments											
Blood sampling for vortioxetine quantification	√					√				√	
Safety Assessments											
Adverse events	√ ^e	√	√	√	√	√	√	√	√	√	√ ^f
Blood and urine sampling for clinical safety laboratory tests ^j	√ ⁱ					√				√	
Vital signs	√ ^d	√	√	√	√	√		√		√	
Weight and height	√ ^d					√				√	
ECGs	√					√				√	
Examinations (physical and neurological)	√ ^d					√				√	
Menstrual cycle	√ ^d									√	
Tanner staging	√ ^d									√	
C-SSRS	√ ^d	√	√	√	√	√	√	√	√	√	
GBI (mania subscale)	√		√		√	√		√		√	
Other Study Procedures											
IMP dispensed	√	√	√	√	√	√	√	√	√		
IMP returned and IMP accountability	√	√	√	√	√	√	√	√	√	√	

Recent and concomitant medication	✓ ^e	✓	✓	✓	✓	✓	✓	✓	✓	✓	
Pregnancy test ^g	✓					✓				✓	
Drug and alcohol screen ^h											

CDRS-R = Children depression rating scale revised version; CGI-I = Clinical Global Impression – Global Improvement; CGI-S = Clinical Global Impression – Severity of Illness; C-SSRS = Columbia-Suicide Severity Rating Scale; eCRF = electronic case report form; ECG = electrocardiogram; GBI: General Behaviour Inventory; IMP = investigational medicinal product; K-SADS-PL = The Kiddie-Schedule for Affective Disorders and Schizophrenia for School-aged Children, Present and Lifetime version; PQ-LES-Q = Pediatric Quality of Life Enjoyment and Satisfaction Questionnaire – Patient rated; SAE = serious adverse event

- a Patients from Study 12712A who are in remission after 8 to 12 weeks of open-label treatment in study 12712A will enter directly into the Randomization Visit of this study.
- b This can be a telephone contact, unless an SAE has occurred since the last visit or unless there was a clinically significant abnormal safety laboratory test value at the last visit. In such cases, safety follow-up(s) must be scheduled to allow for a medical examination and/or blood sampling. Further safety follow-up visits beyond 30 days may be needed as judged by the investigator (if further safety follow-up visits are performed, these must be recorded in the patient's medical record, and not in the eCRF).
- c If the date of a patient visit does not conform to the study plan, subsequent visits should be planned to maintain the visit schedule relative to the Randomization Visit (Visit 8). Consider that the number of days between 2 visits must not exceed the number of days for which the patient has been dispensed IMP.
- d For 12712A-patients, last available values from assessments and procedures (efficacy/safety, and use of concomitant medication) performed at either Visit 7 (Week 8) and/or Visit 8 (Week 10), or Visit 9 (Week 12) in Study 12712A will be the Randomization Visit values for this study, when applicable. For patients who rollover at Visit 7 or Visit 8, weight, height, Tanner staging, menstrual cycle, and examinations should be done at the Randomization Visits.
- e For 12712A-patients, ongoing AEs and concomitant medication from study 12712A will be used for eCRF.
- f Only for AEs ongoing at Completion/Withdrawal and new SAEs
- g If the patient is a female patient of childbearing potential (defined as females aged ≥ 10 years old and younger girls who, at the discretion of the investigator, were deemed to be of reproductive potential), a urine pregnancy test is to be performed at randomization, Visit 13 (Double-Blind Treatment Period Week 10) and at Completion/Withdrawal Visit. Additional pregnancy tests during the study will be performed according to local requirements.
- h It is not mandatory to screen for drugs and/or alcohol. However, it can be performed at any visit, at the discretion of the investigator.
- i Only for 12712A-patients who rollover into Double Blind phase.
- j The hormones panel is to be collected at Visit 8 (for 12712A-patients) and Completion/Withdrawal (for all patients).

